Dose Selection: This study will assess the effects of psychotherapy sessions assisted by two therapeutic doses. The first experimental dose will use 75 mg of MDMA followed 1.5 to 2 hours later by an optional dose of 37.5 mg. During the second Experimental Session an initial dose of either 100 mg or 75 mg will be administered followed by an optional supplemental half-dose 1.5 to 2 hours after the initial MDMA dose. The default dose for the second session will be 100 mg (followed by an optional supplemental half-dose), however if, after discussion with the Clinical Investigators, each participant may be permitted to stay at 75 mg (followed by an optional supplemental half-dose) for the second session.

Table i: Dose Selection

Initial MDMA Dose	Optional Supplemental MDMA Dose	Cumulative (Initial + Optional) MDMA Dose
75 mg	37.5 mg	112.5 mg
100 mg	50 mg	150 mg

MDMA appears to temporarily reduce fear and increase interpersonal trust, without clouding the sensorium or inhibiting access to emotions. MDMA may catalyze therapeutic exposure by enhancing the ability to tolerate negative or threatening emotional states and allowing patients to stay emotionally engaged without being overwhelmed by the intense emotions surrounding their condition.

The active dose of MDMA to be used in this study is similar to the full dose of 125mg followed by a supplemental half dose of 62.5mg used in previous studies in the U.S., Switzerland, and Israel. Previous researchers have also used doses within this range [10-19]. Prior to the scheduling of MDMA, similar doses and regimens were used in psychotherapy [20-22]. The MDMA doses to be used in this study have been used in previous studies sponsored by MAPS.

The initial active doses are expected to produce all the commonly reported effects of MDMA, including changes in affect, mood, and cognition and changes in feelings of interpersonal closeness and trust. The supplemental dose will prolong subjective drug effects without producing physiological effects any greater than peak effects occurring after the initial dose.

Protocol Objectives: The overall objective of this study is to explore the safety and estimate the effect size of efficacy for MDMA-assisted psychotherapy in conjunction with CBCT on PTSD symptoms in PTSD+ participants and relationship functioning in both participants.

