2.4 Rationale of Dose Selection

This study will assess the effects of psychotherapy sessions assisted by two therapeutic doses. The first experimental dose will use 75 mg of MDMA followed 1.5 to 2 hours later by an optional dose of 37.5 mg. During the second Experimental Session an initial dose of either 100 mg or 75 mg will be administered followed by an optional supplemental half-dose 1.5 to 2 hours after the initial MDMA dose. The default dose for the second session will be 100 mg (followed by an optional supplemental half-dose), however if, after discussion with the Clinical Investigators, each participant may be permitted to stay at 75 mg (followed by an optional supplemental half-dose) for the second session.

Table 2: Dose Selection

Initial MDMA Dose	Optional Supplemental MDMA Dose	Cumulative (Initial + Optional) MDMA Dose
75 mg	37.5 mg	112.5 mg
100 mg	50 mg	150 mg

MDMA appears to temporarily reduce fear and increase interpersonal trust, without clouding the sensorium or inhibiting access to emotions. MDMA may catalyze therapeutic exposure by enhancing the ability to tolerate negative or threatening emotional states and allowing patients to stay emotionally engaged without being overwhelmed by the intense emotions surrounding their condition.

The active dose of MDMA to be used in this study is similar to the full dose of 125mg followed by 62.5mg supplemental dose used in previous studies in the U.S., Switzerland, and Israel. Previous researchers have also used doses within this range [10-19]. Prior to the scheduling of MDMA, similar doses and regimens were used in psychotherapy [20-

22]. The MDMA doses to be used in this study have been used in previous studies sponsored by MAPS.

The initial active doses are expected to produce all the commonly reported effects of MDMA, including changes in affect, mood, and cognition and changes in feelings of interpersonal closeness and trust. The supplemental dose will prolong subjective drug effects without producing physiological effects any greater than peak effects occurring after the initial dose.

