6.4 Drug Storage and Handling

MDMA is a Schedule I compound and will be stored and handled in compliance with all relevant federal and state regulations. In accordance with these requirements, the Schedule I license holder will be responsible for storing, dispensing, and administering the MDMA. It will be stored in a secure safe in accordance with federal and state regulations.

IP will only be removed for a single Experimental Session at a time and will be administered orally at the treatment site. All doses administered will be recorded on the appropriate accountability and administration logs. Only the initial dose is required to be given at each Experimental Session. Supplemental doses are provided for each

Experimental Session but are optional to use. In addition, the clinical titration doses with corresponding supplemental dose are provided for the second Experimental Session. The dose to be used at the second session is at the discretion of the CI.

The Schedule 1 License Holder will dispense the appropriate container number for each Experimental Session. If an optional dose is not administered, the unused capsules will be kept in their respective inner envelopes inside of the primary container in the safe for drug accountability.

Records pertaining to the use of scheduled, regulated compounds will be maintained in accordance with relevant federal and state regulations.

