Qualitative safety analyses will examine adverse events, concomitant medications, and spontaneously reported reactions by summary tables listing maximum severity and

duration, as well as frequencies and percentages, tabulated overall and by PTSD+ participants and CSO participants. Quantitative safety analyses will examine vital signs, changes in Tinnitus and/or Pain, SUD, and C-SSRS, with comparisons made between by PTSD+ participants and CSO participants for effect of PTSD on safety measures.

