# 2.0 Background

This is a feasibility and method development study to examine combining CBCT and MDMAassisted psychotherapy in subjects with chronic PTSD (PTSD+ participant) and a Concerned Significant Other participant (CSO participant) without a current PTSD diagnosis but with related psychological distress. Eligible and enrolled participants will undergo a 2-month treatment course in dyads that includes CBCT, as described in Monson and Fredman's (2012) manual [1], integrated with elements of the Treatment Manual for MDMA-assisted psychotherapy to guide the incorporation of CBCT and MDMA [2]. This study will serve as a guide for reseasrchers to test the feasibility of two therapeutic doses of MDMA: (a) 75 mg + optional 37.5 mg supplement in Experimental Session 1 and (b) 100 mg + optional 50 mg (default dose) or 75 mg + optional 37.5 mg supplement in Experiemntal Session 2, plus psychotherapy sessions and non-drug CBCT sessions for PTSD (Tables 1& 2). The initial active doses are expected to produce all the commonly reported effects of MDMA, including changes in affect, mood, cognition, feelings of interpersonal closeness, and trust. The supplemental dose will prolong subjective drug effects without producing physiological effects any greater than peak effects expected after the initial dose. Each therapy team will have one therapist professionally trained and experienced in MDMA-assisted psychotherapy and the other therapist in CBCT. Whenever possible both therapists will have had training in both methods.

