#### **Protocol Deviations**

All protocol deviations will be included as a categorized listing. Safety and mITT analyses will include all enrolled dyads with all available data. Dyads with major deviations will be excluded from the per protocol analyses. Possible protocol deviations include the following seven categories:

- Subject entered study but did not meet criteria
- Subject developed withdrawal criteria but was not withdrawn
- Subject received excluded concomitant treatment
- Protocol procedure not performed per protocol
- Subject received incorrect treatment or incorrect dose
- Protocol procedure performed out of range
- Miscellaneous

The number of dyads in each protocol deviation category listed below will be summarized by MDMA group, and individual subjects will be listed in the appendix.

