## 6. Safety Analyses

The primary measure of safety will be reports of adverse events. Adverse events are Treatment Emergent Adverse Events (TEAE) defined as those AE's that occurred after dosing and existing medical history diagnoses that worsened during the study. Verbatim terms on case report forms will be mapped to preferred terms and system organ classes using the MedDRA dictionary. For incidence reporting if a subject has more than one AE mapped to the same preferred term, that AE will be reported only once using the highest severity and closest relationship to study drug. Subject incidence of AEs will be displayed by group and by system organ class. AEs will also be summarized by severity. Subject incidence of SAEs will also be displayed. In addition to the listing of all AEs, a listing of SAEs and a listing of AEs leading to discontinuation of study drug will be included.

Summary tables of frequency listings of commonly reported AEs (Spontaneously Reported Reactions) mapped to preferred terms will be displayed during and after each experimental session by PTSD+ participants and CSO participants. Additional safety measures will be analyzed as follows:

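### PTSD+ versus CSO safety differences are to be read as an effect of PTSD, although session 2 dose is chosen per participant and no safety table is shown by dose received

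*Protocol*

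**What the plan says.** **Dose.** Every participant starts session 1 on 75 mg (Protocol Tables 1 and 6). For session 2 the default is 100 mg, but "each participant may be permitted to stay at 75 mg (followed by an optional supplemental half-dose) for the second session" (Protocol 2.4). Protocol 6.4 adds: "The dose to be used at the second session is at the discretion of the CI". The same section requires only the initial dose at each session and leaves the supplement optional. Drug is packed separately for each participant and session (Protocol 6.2.3).

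**Safety analysis, Protocol 12.0.** Adverse events, medications and reactions are tabulated overall and by role. Vital signs, tinnitus or pain, SUD and C-SSRS are analysed with "comparisons made between by PTSD+ participants and CSO participants for effect of PTSD on safety measures". Dose is not mentioned.

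**Safety analysis, SAP section 6, Safety Analyses.** For adverse events: "Subject incidence of AEs will be displayed by group and by system organ class". They are also summarised by severity. Spontaneously reported reactions are shown by session and role, SUD by session and role, vital signs by time point, and C-SSRS and General Well-being by role. In the adverse event incidence table a preferred term counts once per subject, at its highest severity.

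**Where dose does appear.** SAP, Subject Disposition and Dosing Summary, reports timing of doses and total milligrams by analysis population and role. SAP, Protocol Deviations, has a table that "will be summarized by MDMA group".

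**The concern.** The protocol attaches a cause to the role contrast: differences are to be read as due to PTSD. Nothing in the design balances dose between the two roles after the first 75 mg of session 1. If PTSD+ participants move to 100 mg, or take the supplement, more or less often than their partners, part of any difference in blood pressure, distress or reactions at those times belongs to dose. No planned output would separate the two.

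This matters because safety is part of the overall objective (Protocol 3.0), and the SAP says the results will help design a larger study of safety and efficacy. Protocol 7.2.2 also makes a dose-specific statement, that the highest dose is expected to raise blood pressure and heart rate temporarily. No planned table looks at that outcome by dose received.

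**Working it through.** The plan gives no figure on this point. Its one power figure, 62% for the paired CAPS test (Protocol 12.1), reproduces at 61.6% from a noncentral t with 9 degrees of freedom and noncentrality 0.8 × √10. It has no bearing here.

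**1. Dose levels the plan allows** (Protocol Tables 1 and 2)
- Session 1: 75, or 75 + 37.5 = 112.5 mg.
- Session 2: 75, 100, 75 + 37.5 = 112.5, or 100 + 50 = 150 mg. The range is 150/75 = 2-fold.

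**2. What each safety output is split by**

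| Output | Split by | By dose received? |
|---|---|---|
| Adverse events | group (undefined), organ class, severity | No |
| Reactions | session, role | No |
| SUD | session, role | No |
| Vital signs | time point (SAP); compared by role (Protocol) | No |
| C-SSRS, General Well-being | role (C-SSRS also by time period) | No |
| Milligrams given | population, role | Not linked to any outcome |

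**3. Size of the mixing.** Let k of 10 PTSD+ and m of 10 CSO participants take 100 mg at session 2. Let D be the true difference in outcome between 100 mg and 75 mg, and suppose role has no effect. Then:

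spurious role gap = (k − m)/10 × D

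The documents give neither the split nor D, so what follows is assumed. Take k = 9 and m = 5, meaning 1 and 5 participants stay at 75 mg, and a reaction rate of 30% at 75 mg.
- Rate at 100 mg of 40%: PTSD+ 0.9 × 40 + 0.1 × 30 = 39%; CSO 0.5 × 40 + 0.5 × 30 = 35%. Gap 4 points.
- Rate at 100 mg of 60%: PTSD+ 0.9 × 60 + 0.1 × 30 = 57%; CSO 0.5 × 60 + 0.5 × 30 = 45%. Gap 12 points.
- k = m: gap 0, whatever D is.

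Mean initial dose in this example is (9 × 100 + 75)/10 = 97.5 mg versus (5 × 100 + 5 × 75)/10 = 87.5 mg. For scale, the standard error of the 12-point gap, treating the roles as independent, is √(0.57 × 0.43/10 + 0.45 × 0.55/10) = 0.22, or 22 points.

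**4. If the contrast were tested.** The protocol names no test for it. Simulated rejection rates for an unadjusted two-sided t-test at 5% are below (10 versus 10, independent normal outcomes, no true role effect, 20,000 replicates):

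| At 100 mg, PTSD+ vs CSO | D = 0.5 SD | D = 1 SD |
|---|---|---|
| 10 vs 10 | 4.7% | 5.2% |
| 8 vs 5 | 5.6% | 6.8% |
| 10 vs 5 | 7.8% | 15.2% |
| 10 vs 0 | 18.6% | 56.4% |

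Moderate imbalance does little harm. Strong imbalance does a lot.

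**5. A comparison without dose differences is already in the schedule.** Protocol Table 5 gives the initial dose at 10:00, SUD at 11:00, and vital signs with SUD at 11:30, when the optional supplement is given. Protocol 5.1.2 requires vital signs before the supplement. At session 1 these readings follow the same 75 mg in everyone. C-SSRS is scheduled before drug and about six hours after, so it has no reading in this window.

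**The case against.** Several stronger readings are tempting, and the documents do not support them.

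- *The planned tables cannot describe either dose.* A reader might infer this from the SAP's aim to "test the feasibility of two therapeutic doses of MDMA". But SAP 2.0 goes on to define the doses largely by session, the second being "100 mg + optional 50 mg (default dose) or 75 mg + optional 37.5 mg supplement". Reactions and SUD are shown by session, so the flexible regimen as used is described. What is missing is session 2 split by the dose actually taken.
- *Pooled session 2 rates understate what happens at 100 mg.* That assumes those who stay at 75 mg react less. If they stay because session 1 went badly, pooling could err the other way.
- *Adverse events are tabulated by a group that does not exist.* The safety objectives speak of both groups, apparently meaning PTSD+ and CSO, so *by group* is undefined and probably means role. Only *MDMA group* plainly has a single level, and that is the deviations table.
- *The once-per-subject rule hides all session differences.* It governs adverse event incidence. Reactions are displayed separately for each session.

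Beyond these, the study team can fairly say that a dose imbalance between roles would be visible in the exposure summary, that listings cover only 20 people, and that a full split of session 2 by dose, supplement and role makes 8 cells averaging 20/8 = 2.5 participants. Contrasts within dose received also condition on a choice made after session 1 and so carry selection of their own. All of this stands, and it limits the remedy to description. It does not rescue the causal label on the role contrast, and the exposure summary would show an imbalance without showing its effect on any safety outcome.

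**Conclusion.** The point holds in limited form. Protocol 12.0 assigns role differences in safety to PTSD without regard to dose, and no safety output in either document is shown by dose received. The problem is confined to session 2 and to readings after the supplement. It is absent from session 1 readings before the supplement.

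Size and direction cannot be known from the documents. In the illustration the spurious gap is 4 to 12 points, which rests on an assumed 1 of 10 versus 5 of 10 staying at 75 mg and assumed reaction rates. It is zero with matching splits and small against sampling error with 10 per role. That the supplement varies person by person is inferred from its being optional and from the packaging, since the documents do not say who decides.

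This is an inexpensive improvement to the analysis of an exploratory pilot. It does not challenge the design and takes no view on which dose is right.

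**What to change.** 1. **Role comparison.** For vital signs and SUD, make session 1 readings after the initial dose and before the supplement the main PTSD+ versus CSO comparison. Describe every other role contrast, including C-SSRS, as a difference by role and drop the attribution to PTSD. Confirm that CSO participants complete SUD in that window: Protocol 5.2.4 names only the PTSD+ participant for repeated SUD, whereas 5.1.2 and Table 4 list both, so these passages need reconciling.
2. **Session 2 tables.** Add descriptive tables of reactions, vital signs, SUD and adverse events by initial dose received, with supplement taken shown. Count a preferred term once per subject per session. State that dose was chosen after session 1, so within-dose contrasts may reflect selection.
3. **SAP wording.** Replace *by group* in Safety Analyses with PTSD+/CSO role, and drop *MDMA group* from Protocol Deviations.
4. **Reason for dose.** Record why each session 2 dose was chosen, if this is not already captured. The CRF is not among the documents, so it may be.

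The cost is SAP wording, a few tables and possibly one CRF field. Doses are already logged and total milligrams already summarised. The drawback is small cells, so the tables can only describe.

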12.1 Statistical Power

This pilot RCT is the first study of its kind intended to establish preliminary effect size estimates of CBCT combined with MDMA-assisted psychotherapy for PTSD. In the absence of published effect sizes for this new treatment modality, effect sizes were estimated based on prior trials of these individual treatments. In a limited number of small pilot studies, CBCT for PTSD yielded paired-treatment effect sizes of g > 1.0 for improvements in PTSD on the primary outcome measure and co-morbid symptoms. The two completed controlled RCTs of MDMA-assisted psychotherapy for PTSD have yielded effect sizes of g > 1.0 for improvements in PTSD symptoms as well. Assuming that effect size of the combined treatment may be approximately 0.8, estimated power for a within-subject analysis with a significance level of .05 based on a 2-tailed test, is 62% for a sample size of 10 participants for the primary measure, suggesting the potential for an underpowered design, but with some possibility of detecting a within-subject effect due to treatment. Statistical power estimates were not available for secondary and exploratory measures, as they were previously not used in sponsor-supported studies.

13.0 Ethics

This clinical study was designed and shall be implemented and reported in accordance with the ICH Harmonized Guidelines for Good Clinical Practice, with applicable local regulations (including European Directive 2001/20/EC, US Code of Federal Regulations Title 21), and with the ethical principles laid down in the Declaration of Helsinki.

The protocol and the ICF must be reviewed and approved by a properly constituted IRB and FDA before study start. Signed and dated documentation of IRB and FDA approvals must be provided to the sponsor. Prior to study start, the Clinical Investigator is required to sign a protocol signature page confirming their agreement to conduct the study in accordance with these documents and all of the instructions and procedures found in this protocol and to give access to all relevant data and records to the sponsor.

14.0 Informed Consent

The main licensed therapists are responsible for obtaining informed consent in adherence to GCP and according to applicable regulations prior to entering the participant into the trial. Information about the study must be given orally and in an understandable form. Written information about the trial will also be provided. The informed consent discussion must be conducted by a person who is qualified according to FDA regulations. The PTSD+ participants and CSO participants should have the opportunity to inquire about details of the MDMA-assisted session and to consider participation.

For all PTSD+ participants and CSO participants the dose of MDMA will be disclosed. This is not a blinded study.

In addition to the explanation of study visits, the information should include that access to original medical records and processing of coded personal information must be authorized. Written consent to take part in the study includes giving the Clinical Investigators permission to view the PTSD+ participant's and CSO participant's recent medical records to assess protocol eligibility, if needed. Information necessary for protocol participation includes past medical history, psychiatric interview, physical examination, and clinical laboratory tests.

Eligible PTSD+ participants and CSO participants may only be included in the study after signing the IRB approved ICF. Informed consent must be obtained before conducting any study-specific procedures (i.e. all of the procedures described in the protocol, including screening activities). The process of obtaining informed consent should be documented in the PTSD+ participant and CSO participant source documents. The therapists will provide a copy of the signed ICF to the dyad and will maintain the original in the ISF. The ICF process may be performed via telemedicine.

The written ICF and any other written information to be provided to PTSD+ participants and CSO participants should be revised whenever important new information becomes available that may be relevant to the dyad's consent. Any revised ICF and written information should receive approval from an IRB before use. The PTSD+ participant and CSO participant should be informed in a timely manner if new information becomes available that might affect the decision to take part in the MDMA-assisted session. The communication of this information should be documented.

PTSD+ participants and CSO participants can withdraw consent at any time without prejudice. If a PTSD+ participant or CSO participant withdraws consent but does not revoke the Health Insurance Portability and Accountability Act (HIPAA) authorization, the Clinical Investigators will have full access to the PTSD+ participant's or CSO participant's medical records, including Study Termination Visit information. If only the HIPAA authorization is revoked, the Clinical Investigators will have full access to all of the medical records prior to the date and time of revocation.

